UPWARD and each UPWARD Supplemental Arm will have a unique study fact sheet. The online study fact sheet will accurately describe the general goals of the study and the nature of the participant's role in the study. Participants will be given the ongoing opportunity to ask any questions regarding confidentiality, participation schedule, or any other aspect of the study in the first call with the MGH team and in all subsequent contacts with study team members. After reading the study fact sheet, study staff will obtain verbal consent for participation. In addition, participants will review key points of the study with study staff, will be provided with contact information and encouragement to contact study staff members with questions via email or phone, and will be encouraged to print and retain personal copies of the study fact sheet. Consented subjects will be sent a copy of the phone consent document. This consent form will include a summary of privacy policies and date of consent. Individuals who do not provide verbal consent will be informed that it is not possible for them to participate in the study and we will provide them with a list of links to depression information websites.

[figure not shown]
To maintain concealment, assignment will occur following the baseline assessment by telephone interview with the MGH team. Assignments will be generated using a random number table with equal probability of assignment to each group in blocks of four, which will guarantee balance for every four subjects. Randomization to study arm will be stratified based on number of prior episodes, antidepressant medication status (on medication or having discontinued at time of randomization), and baseline depressive severity based on PHQ-9 score. Women will be randomly assigned to receive MMB ($n = 300$) or UC ($n = 300$).

Study staff will also obtain contact information for community providers and consent from study participants to be in touch with these providers. This contact information will be used to send a letter describing the study and providing the consult line and availability of study doctors for questions. Additionally, we will reference the MGH Center for Women's Mental Health's website, www.womensmentalhealth.org, as a perinatal resource center that provides evidence-based safe practices for both the study participant and their clinician during pregnancy.

UPWARD Supplemental Arms

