The final 100 participants in the UPWARD sample of 600 individuals will participate in an abbreviated version of the UPWARD procedures. These 100 women will be recruited via the same platform of BabyCenter, screened and enrolled based on the same entry criteria, and similarly randomized to the MMB intervention or Usual Care. However, the only differences will be that these final participants in this group of 100 who are randomized to the treatment group will not receive the coaching that is typically involved in the MMB intervention. This will further investigate our research aims to assess the extent to which this modified version of MMB is still an effective means of preventing depressive relapse in a perinatal population. Moreover, these final 100 participants will not receive any follow-up clinical interviews or relapse determination calls after the initial screening and baseline calls. Participants will be randomized after the baseline call, either through a phone conversation or via email. They will instead be prospectively followed through 3 months postpartum via the same battery and schedule of self-report questionnaires given to the other UPWARD participants through this timepoint. If any participant endorses items 3, 4, or 5 on the C-SSRS via these self-report questionnaires, the same suicidality safety protocol will be triggered as outlined below. The information about the delivery and newborn outcomes that would typically be collected during the 3 months postpartum interview will now be administered as a self-report survey with the rest of the questionnaires for this timepoint.

Table 2. UPWARD Extension Measurement Schedule

UPWARD Study	Baseline	M1	W6	M2	Post-Intervention	M3	M4	M5	3T	M6	M7	M8	3PP
MINI full	x												
MINI mood	x				x				x				x
MADRS	x				x				x				x
EPDS	x	x	x	x		x	x	x	x	x	x	x	x
PHQ-9*	x	x	x	x		x	x	x	x	x	x	x	x
CS-S**	x												
CGI	x				x				x				x
PGI	x	x	x	x		x	x	x	x	x	x	x	x
GAD-7	x	x	x	x		x	x	x	x	x	x	x	x
PSS-10	x					x			x				x
WHODAS 2.0	x					x			x				x
CSQ-8 (UC)	x					x							
CSQ-8 (MMB)						x							
CTQ	x												
PROMIS	x												
FFMQ	x		x			x							
RRS	x		x			x							
SCS	x		x			x							
SSQ-SF	x					x							x
RSQ-MEP	x												
LEL	x												
LEIDS-R	x		x			x							
EQ	x		x			x							
CSI	x												
AToM	x					x			x				x
PSA	x		x			x			x				
PSQI	x					x							x
Positive Mood Diary	x		x			x							

DPES Joy Subscale	x		x		x					x
CERTS Unresolution Subscale	x									

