In UPWARD, UPWARD Extension and UPWARD-S, if suicidality is endorsed with a score of greater than 1 on EPDS item #10 or PHQ-9 item #9 or on any of the self-report questionnaires (such as the SITBI or CCM), subjects will be prompted to complete the CS-S to assess risk of suicidality. Study subjects will also be given the national suicide [contact]) and informed that answers to online questionnaires are not monitored in real time. A positive score on questions 3, 4, or 5 on the CS-S, indicating intention or plan for suicidality, will prompt a safety call by study physicians. Suicidality expressed during the course of clinical or qualitative interviews, either through discussion, endorsement of the suicidality item on the MINI mood module, endorsement of items 3, 4, or 5 on the suicidality module of the MINI, or via scoring >2 on the MADRS item 10, will prompt study staff to complete the CS-S with the participant. A positive score on items 3, 4, or 5 of the CS-S administered by staff will also prompt a safety call by study physicians. In addition, subjects will be told by study staff to call their community providers and go to their nearest emergency room. Endorsement of items 3-5 on the CS-S prompting a physician safety call has been the threshold used in previous studies at the collaborating site (University of Colorado Boulder). As this is a community-based study with collaboration from community physicians, these providers dictate treatment. We will notify community providers directly via phone or fax within 24 hours from report of positive scores on CS-S items 3-5.

VI. BIOSTATISTICAL ANALYSIS

Preliminary Analyses: Differences between the MMB and UC in demographic characteristics and depression related characteristics (e.g., symptom severity, comorbidity) will be assessed using Chi-square test for binary variables, Cochran Mantel Haenszel tests for categorical variables, and t-tests for continuous variables. Variables that show significant group differences and predict outcome will be entered in analyses as covariates; AD exposure will be included as a covariate. All participants will be considered evaluable for analysis (intent-to-treat sample). Significance levels will be evaluated at $p < .05$, and effect sizes reported.

Analysis for Specific Aim #1: To test the relative risk for depressive relapse and reduction of symptom burden between women randomized to digital MMB or UC.

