To test target engagement, we will use the same HLM methods described above to compare differences between MMB and UC in change in the putative targets during the intervention period. To test target validation, we will use recent statistical developments that apply formal causal inference concepts to mediation analyses. Causal mediation approaches address violations of the assumption of sequential ignorability (e.g., no confounding/randomization of the mediator) that is required for unbiased estimates of the M (mediator) \rightarrow Y (outcome) relationship. Addressing the issue of sequential ignorability yields unbiased estimates of the natural direct effect (NDE = the non-mediated effect of reduction of depressive related outcomes) and the natural indirect effect (NIE = the component of the intervention that seems to proceed through the respective mechanisms), with Total Effect = NDE + NIE.²⁷ A high NIE indicates that the subsequent outcomes are mediated through time-lagged mechanisms improvements. We have experience implementing these models which fall under the classification of marginal structural models (MSM), principal stratification (PS), structural nested mean models (SNMM), and rank preserving models (RPM),²⁸⁻³⁰ which we will apply for each putative target individually. Sensitivity analyses will be implemented using approaches outlined by Ding and VanderWeele.³¹

Power Analysis for Specific Aim #1: To test the relative risk for depressive relapse and reduction of symptom burden between women randomized to digital MMB or UC.

For the analysis of rates of relapse, in our efficacy study of MBCT,³² pregnant women who received MBCT evidenced approximately 30% lower rate of relapse than UC. In estimating the difference in relapse rates between MMB and UC, accommodating the sample size required to address Aim 2, N = 600 participants is required for randomization. With N=600, we have 95.5% power to detect a 20% difference in relapse rates (which is smaller than what we observed in our efficacy study) and allowing for 30% attrition, which is higher than attrition in our efficacy study of MBCT with pregnant women (15%) and lower than attrition in our digital delivery of MBCT work (approximately 40%).

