For the continuous outcomes, using the method described by Ahn et al. to derive formulas for power estimation of linear mixed models,³³ power calculations can be made for repeated measures designs under specified assumptions. Based on a sample size of 300 per group, assuming 30% attrition for a total of 175 per arm randomized, with an alpha-level at 0.05 based on a 2-tailed test, assuming a within correlation of 0.5, we have power of 86.5% to detect an effect size of .25. Varying the effect size, we have 95.7%, 99.0%, and 99.8% power for effect sizes of 0.3, 0.35, and 0.4 respectively, which are much smaller than the d=0.70 effect size

observed in our efficacy study of MBCT with pregnant women,³⁴ indicating that we are sufficiently powered.

Power Analysis for Specific Aim #2: To explore the specific benefit of MMB relative to AD discontinuation and questions regarding personalization that are of strong interest to pregnant women and their healthcare providers.

H2a: Comparison of MMB to UC among women who discontinue AD: Anticipating balance across the 4 cells (randomized to MMB or UC; choice of discontinue AD or maintain AD), with approximately 300 participants across the two cells of interest, we have 82.8% power to detect a 23% difference in relapse rates with 30% attrition, which is smaller than what would be expected comparing the relapse rates among women who received MBCT (19%) in the [name] et al. study of MBCT with pregnant women³² to the rate of relapse among women who discontinued AD during pregnancy (66%) in the Cohen et al. prospective study¹⁰).

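### The relapse powers of 95.5% (Aim 1) and 82.8% (H2a) do not follow from the sample sizes and attrition stated beside them

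*Combined protocol and SAP*

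**What the plan says.** Section VI, Power Analysis for Specific Aim #1, says that 600 women must be randomised and continues: "With N=600, we have 95.5% power to detect a 20% difference in relapse rates", "allowing for 30% attrition". Section IV gives 1:1 allocation, 300 per arm.

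The power analysis for H2a (Specific Aim #2) expects the four cells of arm by antidepressant choice to be balanced, with about 300 women in the two cells being compared: "across the two cells of interest, we have 82.8% power to detect a 23% difference in relapse rates with 30% attrition".

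Neither statement gives a usual-care (UC) relapse rate or names a test. Alpha comes from the Preliminary Analyses paragraph: "Significance levels will be evaluated at $p < .05$, and effect sizes reported". Two-sided testing is stated only for the continuous outcome: "with an alpha-level at 0.05 based on a 2-tailed test". That same paragraph starts from 300 per group, applies 30% attrition and arrives at 175 per arm.

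Section V, UPWARD Extension, sets apart "The final 100 participants in the UPWARD sample of 600 individuals". It says these women have no follow-up clinical interviews or relapse determination calls after screening and baseline, and are followed by self-report to 3 months postpartum.

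**The concern.** These are the only powers given for the relapse outcome. A reader who applies the stated attrition to the stated N gets clearly higher power for both comparisons, so either the N or the power is wrong as written.

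Which one it is matters. The Aim 1 analysis rates relapse by the MINI, through 6 months postpartum. If the Extension women do not contribute MINI-rated follow-up, about 500 women may be the true basis for that analysis. The printed powers could then be roughly right and the printed N wrong. If all 600 count, the powers are wrong. The plan does not let the reader decide.

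**Working it through.** **Inputs**
- Aim 1: 600 women, 1:1, 30% attrition. 600 × 0.7 / 2 = 210 per arm.
- H2a: about 300 women in two balanced cells, 30% attrition. 300 × 0.7 / 2 = 105 per cell.
- Differences: 20 and 23 percentage points, read as absolute.
- Alpha 0.05, taken as two-sided. This is an assumption for relapse; one-sided testing would only raise power.
- Base rate: not stated, so every possible UC rate was scanned with the difference held fixed.

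**Formula** (n per group, relapse rates p1 and p2, mean p̄, d = p1 − p2)
- SE0 = √(2p̄(1 − p̄)/n); SE1 = √((p1(1 − p1) + p2(1 − p2))/n)
- Power = Φ((d − c − 1.96·SE0)/SE1), with c = 0 uncorrected and c = 1/n with continuity correction.
- The minimum over base rates falls where the two rates straddle 50%: 60% v 40% for Aim 1 and 61.5% v 38.5% for H2a.

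**Attempt to reproduce the stated powers at the stated sizes**

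Aim 1, n = 210: SE0 = √(0.5/210) = 0.0488; SE1 = √(0.48/210) = 0.0478.
- Uncorrected: (0.2 − 0.0956)/0.0478 = 2.18, power 98.5%.
- Corrected: (0.2 − 0.0048 − 0.0956)/0.0478 = 2.08, power 98.1%.

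H2a, n = 105: SE0 = √(0.5/105) = 0.0690; SE1 = √(0.47355/105) = 0.0672.
- Uncorrected: (0.23 − 0.1353)/0.0672 = 1.41, power 92.1%.
- Corrected: (0.23 − 0.0095 − 0.1353)/0.0672 = 1.27, power 89.8%.

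Other tests give the same picture:

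| Test | Aim 1, 210 per arm | H2a, 105 per cell |
|---|---|---|
| Pooled, uncorrected | 98.5% | 92.1% |
| Unpooled | 98.7% | 92.9% |
| Arcsine | 98.5% | 92.0% |
| Continuity-corrected | 98.1% | 89.8% |
| Log-rank, Schoenfeld | 98.8% | 93.3% |
| Log-rank, Freedman | 98.4% | 91.4% |
| Fisher exact | 97.9% | 89.0% |
| **Stated in the plan** | **95.5%** | **82.8%** |

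All rows except the last two are minima over all base rates. Fisher was evaluated at selected rates, and the lowest value found is shown. No row reaches the stated figure.

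**Same formula on a 250-per-arm basis**

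N = 500 less 30% leaves 175 per arm. 250 women for H2a less 30% leaves 87.5 per cell.

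| | Corrected | Uncorrected | Stated |
|---|---|---|---|
| Aim 1, n = 175 | 95.6% | 96.55% | 95.5% |
| Aim 1, n = 174 | 95.5% | 96.5% | 95.5% |
| H2a, n = 87.5 | 83.1% | 86.7% | 82.8% |
| H2a, n = 87 | 82.8% | 86.5% | 82.8% |

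One method therefore matches both figures to within rounding of n.

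**Trace in the text.** In the continuous-outcome paragraph, 300 × 0.7 = 210, but the plan prints 175, which is 250 × 0.7.

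**The case against.** The N = 500 explanation is reverse-engineered. The plan names neither a test nor base rates, and its relapse analysis is Cox and Fine–Gray, not a comparison of two proportions. The exact match needs a continuity correction, the least favourable rates and slight rounding down of n. Without the correction, H2a on 250 women gives 86.5–86.7% and does not match. Other departures also come close at the stated sizes: an alpha of 0.0167 without correction gives 95.9% and 83.3%, though the plan says 0.05. This part of the objection stands: 250 per arm is an inference, and it cannot be said that the figures reproduce only there.

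A reader might also infer that the powers were meant for the first 500 women. No passage says so. The Extension text is not linked to power, the Aim 1 paragraph says 600 are required, and the H2b paragraph works from 600 with 150 per cell.

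A further tempting reading is that the 20% and 23% are relative reductions, which would mean much lower power. The H2a paragraph sets its 23% against relapse rates of 19% and 66%, which reads most naturally as an absolute gap. A relative reading comes near the stated figures only with a UC rate around 80% (95.7% and 84.0%), and the highest rate in the documents is 66%.

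Finally, the error at the stated sizes understates power, and the plan ties 600 partly to the needs of Aim 2. That also stands and limits the impact. None of it makes 95.5% or 82.8% follow from the inputs printed beside them.

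**Conclusion.** The point holds as a mismatch between stated power and stated size. With 30% attrition, two-sided alpha 0.05, an absolute difference and balanced cells, Aim 1 has at least about 98% power where the plan says 95.5%. H2a has at least about 89–90% where it says 82.8%. The gaps are about 2 to 3 points and 6 to 10 points, and the missing base rates cannot close them.

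A 250-per-arm basis is the likely source, supported by the numerical match and by the 175 per arm, but it is not documented.

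If all 600 women contribute to the relapse analysis, the error is conservative and the sample size is not threatened. If the Extension's lack of follow-up interviews and relapse calls leaves about 500 with MINI-rated relapse, the printed powers are about right on the inferred method and the N is wrong. Table 2 still lists follow-up MINI mood assessments for the Extension, contrary to its text, so the documents do not settle which applies. This is a reporting correction that should be made, with high confidence in the mismatch and less in its cause.

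**What to change.** Choose one basis and state it:

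- **All 600 (about 300 for H2a):** restate the powers as 98.1% and 89.8% with a continuity-corrected test, or 98.5% and 92.1% uncorrected. These are minima over base rates; replace them with exact values once a UC rate is given.
- **About 500 (about 250 for H2a):** keep powers close to those printed, and say that they refer to about 175 women per arm and about 87 per H2a cell after attrition.

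In either case, give the assumed UC relapse rate and the test, and say that the difference is absolute. Reconcile with the chosen basis the 175 per arm in the continuous-outcome paragraph, the requirement for 600 under Aim 1, and the 600 and 150-per-cell figures under H2b. State whether the Extension women enter the MINI-based relapse analysis.

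The cost is rewording a few sentences in Section VI and rerunning short calculations. Enrolment does not change.

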MGH physicians with perinatal psychiatry expertise will be available via a consult line for community providers of participants enrolled in the UPWARD Study and UPWARD-S. Throughout the study, they will answer questions regarding psychiatric medications and possible treatment options for individual patients determined by their community provider.

MGH study staff trained in interviewing techniques will administer the baseline, qualitative, post-intervention, third trimester, 3 months postpartum, and 6 months postpartum interviews completed for enrollees in UPWARD and UPWARD-S. Those enrolled in UPWARD Extension will complete only the screening and baseline calls. Participants will then be randomized either over the phone or via email. Baseline clinical instrument results will be reviewed and confirmed by study principal investigators to ensure eligibility. We will send a birth acknowledgement by regular mail, email, or both after delivery, and at periodic times during the study, we will send reminders of study engagement or gifts of nominal value to increase cohort retention.

In the UPWARD Study, in addition to regularly scheduled self-report questionnaires and phone contacts, relapse determination calls will be made to any participant scoring ≥ 15 on the monthly PHQ-9 or ≥ 12 on the EPDS. This relapse determination call will consist of study staff asking about the date of relapse and administering the MINI mood module and MADRS retrospectively to assess depressive symptoms during the time of relapse. If a depressive relapse has already been confirmed via clinical interview with the MINI mood module or the MADRS within a week of completion of self-report answers to either the PHQ-9 or EPDS, no relapse determination call will be made. However, if a depressive relapse is not documented during the clinical interview with the MINI mood module, but follow-up self-report surveys indicate increased depressive symptoms, a relapse determination call will be made.

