For the analysis of rates of relapse, we will examine time to relapse as rated by the MINI during pregnancy and across the 6-month postpartum follow up using survival analysis. Survival rates will be compared using Cox proportional hazard regression and illustrated in Kaplan-Meier curves (Collett, 1994). However, time to attrition is a competing risk that can be related to time to relapse. We will adopt the subdistribution hazard model (SHM) developed by Fine and Gray to account for the possible non-independence of the censoring mechanism.²⁵

For the continuous outcomes, we will use Hierarchical Linear Models (HLM) as our primary analytic model, which will compare change over time between groups on depressive symptom burden using the PHQ-9. HLM is flexible with respect to the nature of change over time (i.e., linear, piecewise linear, loglinear, etc.), and will accommodate the within subject correlation through the inclusion of random effects at the patient-level, accounting for the patient-to-patient deviations. Pattern-mixture models²⁶ will be used to assess whether important estimates (i.e., intervention effects) are dependent on missing data and to provide overall estimates of effects by averaging over the various missing-data patterns.

Analysis for Specific Aim #2: To explore the specific benefit of MMB relative to AD discontinuation and questions regarding personalization that are of strong interest to pregnant women and their healthcare providers.

H2a: Comparison of MMB to UC among women who discontinue AD: Our analysis will be the same as H1 with both the time-to relapse and continuous outcome models. We predict that rates of relapse and symptom burden among women randomized to MMB who discontinue AD will be significantly superior to those randomized to UC who discontinue AD.

H2b: Treatment Selection Algorithm: We predict that the use of a treatment selection algorithm will differentiate two profiles of women based on pre-treatment characteristics (those who are optimally suited to discontinue AD and engage MMB to minimize their risk of relapse, and those who should continue AD to minimize risk of relapse) and that women who are randomized to the algorithm indicated approach will have significantly lower risk of relapse and symptom burden than women who are randomized to their algorithm contraindicated approach.

Analysis for Specific Aim #3: To test the extent to which digital MMB engages putative targets.

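### The continuous-outcome power statement gives 175 per arm where 300 per group less 30% attrition is 210, and the powers built on it cannot be traced to one base

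*Combined protocol and SAP*

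**What the plan says.** All places are in the combined protocol and SAP.

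- **Section VI, Power Analysis for Specific Aim #1, continuous outcomes:** "Based on a sample size of 300 per group, assuming 30% attrition for a total of 175 per arm randomized". With two-sided alpha 0.05 and a within-subject correlation of 0.5, it then states powers of 86.5%, 95.7%, 99.0% and 99.8% for effect sizes of 0.25, 0.30, 0.35 and 0.40.
- **Section IV, UPWARD Study:** "Women will be randomly assigned to receive MMB ($n = 300$) or UC ($n = 300".
- **Section VI, Analysis for Specific Aim #1:** the continuous-outcome model will "compare change over time between groups on depressive symptom burden using the PHQ-9". Relapse is analysed as "time to relapse as rated by the MINI during pregnancy and across the 6-month postpartum follow up".
- **Section VI, relapse power:** "With N=600, we have 95.5% power to detect a 20% difference in relapse rates", allowing for 30% attrition. For H2a, about 300 women in two cells give 82.8% power for a 23-point difference, again with 30% attrition.
- **Section V, UPWARD Extension:** "these final 100 participants will not receive any follow-up clinical interviews or relapse determination calls after the initial screening and baseline calls"; these women are followed by self-report to 3 months postpartum. Prospective Follow-up and Community Outreach agrees: "Those enrolled in UPWARD Extension will complete only the screening and baseline calls". Section VII (Risks and Discomforts) also rules out clinical interviews after baseline. Yet the schedule headed "Table 2. UPWARD Extension Measurement Schedule" still marks the MINI mood module after the intervention, in the third trimester and at 3 months postpartum.

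**The concern.** One sentence gives a starting number, a loss rate and a result that do not agree, and it labels the result as the number randomised. That would be a plain slip if the powers could be recomputed, but the inputs needed to do so are missing. A reader therefore cannot tell whether the planned 30% attrition was applied before the four powers were calculated. If it was, correcting 175 to 210 raises power. If it was not, correcting to 210 lowers the power at the smallest stated effect from 86.5% to below 80%.

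There is a second trap in the repair. Writing 210 into the relapse powers as well would be wrong if the final 100 women have no MINI follow-up, since relapse is rated by the MINI.

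**Working it through.** **1. The attrition step.** Inputs from the power text: 300 per group, 30% attrition.
- 300 × (1 − 0.30) = 210 per arm.
- 175 / 0.70 = 250 per arm, that is N = 500.
- 1 − 175/300 = 41.7%.

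So 175 follows from 250 per arm at 30%, or from 300 at 41.7%, but not from the two figures printed beside it.

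**2. Reproducing the four powers.** Stated inputs: two-sided alpha 0.05, correlation 0.5, effect sizes d. I used power = Φ(d·√(n_eff/2) − 1.96), with n_eff = n/v. The variance factor v depends on a design that the plan does not give, so these are assumptions:
- mean of k measures: v = (1 + (k − 1)·0.5)/k; for k = 6, v = 3.5/6 = 0.5833;
- change score: v = 2(1 − 0.5) = 1; a single measure also has v = 1;
- linear slope over k equally spaced measures on a 0–1 time scale, compound symmetry, d as the end-of-study difference: v = 0.5/Σ(t − t̄)²; for k = 8, v = 0.5833.

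| Base per arm | Assumed design | n_eff | d=0.25 | 0.30 | 0.35 | 0.40 |
|---|---|---|---|---|---|---|
| Stated in plan | not given | – | 86.5% | 95.7% | 99.0% | 99.8% |
| 175 | mean of 6, or slope over 8 | 300 | 86.47% | 95.68% | 99.00% | 99.84% |
| 300, no attrition | one measure or change score | 300 | 86.47% | 95.68% | 99.00% | 99.84% |
| 210 | mean of 6, or slope over 8 | 360 | 91.8% | 98.1% | 99.7% | 100.0% |
| 210 | one measure or change score | 210 | 72.6% | 86.7% | 94.8% | 98.4% |

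The second and third rows agree with the plan to the printed decimal and cannot be told apart. The last two rows show what each implies once 210 is used.

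**3. The relapse powers as a cross-check.** The plan gives no relapse rates. I used a pooled two-proportion normal approximation with continuity correction at the least favourable rates (40% vs 60% for 20 points; 38.5% vs 61.5% for 23 points). This only approximates the planned Cox and Fine–Gray analyses. Per-cell numbers are half the per-arm numbers, following the plan's assumption of four balanced cells.

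| Base after 30% attrition | 20-point difference, Aim 1 | 23-point difference, H2a |
|---|---|---|
| Stated in plan | 95.5% | 82.8% |
| 175 per arm; 87 per cell (from N=500) | 95.6% | 82.8% |
| 210 per arm; 105 per cell (from N=600) | 98.1% | 89.8% |

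The stated relapse powers sit on the N=500 row, although the text says N=600.

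**4. Which base relapse can have.** If the Extension text governs, 600 − 100 = 500 women supply MINI-rated relapse. With an even split of the final 100, that is 250 per arm and 250 × 0.70 = 175 after attrition. If the Extension schedule governs, all 600 supply it and 210 per arm applies, though the final 100 then contribute only to 3 months postpartum.

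**The case against.** The strongest reply is that the slip is harmless. The same sentence assumes 30% attrition, prints 175 and names a method for repeated-measures designs, so a calculation at 300 with no attrition and a single measure or two-point change goes against the text. The relapse powers also point to 175. On that reading the correct 210 improves power. Even on the unfavourable reading, power is 86.7% at 0.30, and the plan's reference effect from its efficacy study is 0.70. All participants are to be analysed and the mixed model uses partial data, so 210 is itself a cautious count.

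Most of this stands. It makes the conservative reading the likelier one and keeps the point minor. It does not make 300, 30% and 175 agree, and it does not supply the missing number of measures. That 175 comes from a 250-per-arm calculation is an inference; the plan does not say so.

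A reader might also infer that H2b is short of women, because it sets a required 250 against 150 + 150 = 300 with no attrition allowance. The documents do not support that: they do not say whether 250 counts randomised or analysable women, so no error is shown.

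**Conclusion.** The figure of 175 per arm is wrong for the stated inputs, and this is certain. It should be 300 randomised and 210 remaining, a difference of 35 women per arm. The four continuous-outcome powers are reproducible but not from a unique base. At 210 per arm and an effect size of 0.25, power is 91.8% if they were computed at 175 with six measures averaged, and 72.6% if they were computed at 300 without attrition on one measure or a change score. Both results rest on my assumed designs. The first is more likely, but unproven.

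It would be tempting to conclude that the trial is underpowered for symptom burden. The documents do not show this: the 72.6% needs the less likely base and the smallest listed effect, and every larger listed effect stays above 80%.

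For relapse, the stated 95.5% and 82.8% approximately hold if the Extension text governs; it is then the N=600 label that fails. If the schedule governs, those powers are understated, at about 98.1% and 89.8%. This is a minor correction of a stated figure.

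**What to change.** 1. In the Aim 1 continuous-outcome power text, state 300 per arm randomised and 210 per arm after 30% attrition, or state that the calculation was made for N=500. Restate the four powers from that base, with the number of repeated measures and the effect tested (change, slope or average).
2. Reconcile the UPWARD Extension text, together with the matching statements in Prospective Follow-up and Section VII, with the Extension measurement schedule on MINI follow-up.
3. Then restate the Aim 1 and H2a relapse powers with their own base and the relapse rates used. If the text governs, the base is about 250 per arm, 175 after attrition, assuming an even split of the final 100; the N=600 label should then go. If the schedule governs, use 210 per arm and 105 per cell.

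The cost is a text correction and one rerun of the power calculation. It needs no extra participants and no change of analysis. The only downside is that the continuous-outcome power might have to be stated less favourably, if it was computed without attrition.
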